4.2.1. Withdrawal from Repeat Injection

A withdrawal from repeat injection refers to any subject who does not receive repeat injection(s) (ocriplasmin or sham). Subjects withdrawn from repeat injection(s) should not be withdrawn from the study and, apart from repeat injection-related procedures, should continue all scheduled study visits and procedures until the end of the study to ensure complete follow-up.

The following events should be assessed at Visit 4a (Day 28) and Visit 6a (Day 63), before repeat injection. If any of these events apply, no further injection(s) should be given. For events that are deemed to be temporary, the injection can be postponed, if this is feasible within the protocol-specified study visit interval (refer to [Table 7](#)).

- Severe intraocular inflammation associated with previous injection
- Active intraocular inflammation or infection in either eye at the time of repeat injection
- Any signs or symptoms of lens subluxation associated with previous injection
- Any condition associated with previous injection requiring surgical treatment (*e.g.* new macular hole, worsening of existing macular hole, retinal tear, retinal detachment, IOP increase)
- Persistent presence of subretinal fluid or inner segment / outer segment (IS / OS) junction changes with functional impairment, associated with previous injection, at the time of repeat injection

- Persistent complaint of dim vision, dark adaptation problems or impaired night vision, or afferent pupillary defect, associated with previous injection, at the time of repeat injection
- BCVA decrease \geq 15 letters from baseline or BCVA worse than 20/400, in the study eye, at the time of repeat injection
- Significant ocular trauma in the study eye at the time of repeat injection
- Any other intraocular injection since previous study injection
- Pregnancy
- Subject's individual treatment assignment has been unmasked (emergency unmasking, refer to [Section 3.6.2](#))

In addition, subjects may be withdrawn from repeat injection at any time at the discretion of the Investigator (*e.g.* based on significant abnormalities on ophthalmic examination or functional test associated with previous injection not listed above).

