TG ThromboGenics®	Cover Page
TG-MV-015_Abbreviated SAP_17-JAN-2019	

DOCUMENT TYPE

ABBREVIATED STATISTICAL
ANALYSIS PLAN (SAP)

PROTOCOL TITLE:

A PHASE 2, RANDOMISED,
DOUBLE-MASKED,
SHAM-CONTROLLED, MULTI-CENTRE
STUDY TO EVALUATE THE EFFICACY
AND SAFETY OF OCRIPLASMIN IN
INDUCING TOTAL POSTERIOR
VITREOUS DETACHMENT (PVD) IN
SUBJECTS WITH NON-PROLIFERATIVE
DIABETIC RETINOPATHY (NPDR)
(CIRCLE)

PROTOCOL NUMBER:

TG-MV-015

CLINICALTRIALS.GOV
IDENTIFIER:

NCT02681809

SAP DATE:

17-JAN-2019

ABBREVIATED STATISTICAL ANALYSIS PLAN FOR FINAL ANALYSIS

PROTOCOL TITLE: A PHASE 2, RANDOMISED, DOUBLE-MASKED, SHAM-CONTROLLED, MULTI-CENTRE STUDY TO EVALUATE THE EFFICACY AND SAFETY OF OCRIPLASMIN IN INDUCING TOTAL POSTERIOR VITREOUS DETACHMENT (PVD) IN SUBJECTS WITH NON-PROLIFERATIVE DIABETIC RETINOPATHY (NPDR) **(CIRCLE)**

PROTOCOL NUMBER: TG-MV-015

STUDY PHASE: PHASE 2

EudraCT NUMBER: 2015-002415-15

IND NUMBER: 126449

SPONSOR: THROMBOGENICS NV, [name]
[name]

FINAL PROTOCOL DATE: 04-SEP-2015

AMENDMENT 1 DATE: 13-OCT-2015

AMENDMENT 2 DATE: 28-OCT-2016

Abbreviated SAP 17Jan2019

CONFIDENTIAL

The information contained in this document is CONFIDENTIAL and is the property of ThromboGenics. Except to the extent necessary to obtain informed consent, information may not be disclosed unless such disclosure is required by government regulation or state/local customs or law. No part of it may be transmitted, reproduced, published, or used by anyone without the written permission of ThromboGenics. Persons to whom the information is disclosed must be informed that the information is CONFIDENTIAL and may not be further disclosed by them.

Table of Contents

1. Background	3
2. Objective	3
3. Conventions for Analysis and Computations	3
4. Appendix	7
4.1. Conventions for Imputing Partially Missing and Missing Dates	7

1. Background

This document describes the tables and listings generated for the Final Analysis. The final analysis took place after all subjects completed the Month 24 visit (Visit 11). This document is an abbreviated version of the original SAP, which also contained mock-up tables and listings. In addition, information which is considered of intellectual property nature is not included in this abbreviated version of the SAP.

2. Objective

The objective of this document is to define the set of summary tables and individual data listings that will support the writing of the clinical study report.

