3. Conventions for Analysis and Computations

All Treated Subjects Analysis Set

A single analysis set will be used. The All Treated Subjects analysis set will include subjects who are randomized and receive the first injection of study treatment. Subjects will be assigned to the treatment they receive at the time of the first injection.

Baseline Value

Baseline value is defined as the last non-missing value prior to administration of the first injection of the study drug.

Change from Baseline

Change from Baseline is calculated as the difference between the value at a considered visit minus the Baseline value. Change from Baseline will be missing if either one of the Baseline Value or the value at the considered visit is missing.

Adverse Events

Adverse events are coded using MedDRA version 18.1.

If a subject has multiple occurrences of an AE after an injection, the subject is presented only once in the respective subject count. Events are counted each time in the event column. Ocular adverse events are those that occur in either eye. Events recorded as OU (both eyes) are counted once for the study eye and once for the non-study eye, and are counted as 2 separate ocular events.

Drug related events are events considered by the Investigator with a reasonable possibility that the study treatment caused the event or events with a missing relationship.

Where severity is missing, the adverse event will be assigned to the ‘severe’ category.

AEs will be attributed to the closest injection prior to the occurrence of the event. AEs with a start date corresponding to the date of one of the injections will be attributed to that particular injection.

Treatment Emergent Adverse Events

Treatment Emergent Adverse Events are adverse events with a start date on or post the date of the first injection, or a missing start date.

Concomittant Interventions/Anti-VEGFs

Concomittant Interventions (including Anti-VEGFs) are interventions with a start date on or post the date of the first injection, or a missing start date.

Imputation of Partially Missing Dates

The conventions for imputing partially missing dates are provided in the appendix of this document.

Age Computation

The Date of Birth (DOB) will be imputed to 01JULYYYY where YYYY correspond to the year of birth. The following SAS code will be used for calculating age.

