$$\text{floor}(\text{intck}(\text{'month'}, \text{DOB}, \text{first injection date}) - (\text{day}(\text{first injection date}) < \text{day}(\text{DOB}))) / 12$$

By Visit Layout

In tables summarizing data ‘By Visit’, post-injection 2 and 3 visits will be presented on 2 rows. The first row will be labelled ‘Day/Month xx, Post-Injection 2/3’ and will present data of subjects with 2 or 3 injections, respectively. The second row will be labelled ‘Day/Month xx, Missing Repeat Injection(s)’ and will present data of subjects who did not receive the complete set of repeat injections.

Early Termination Visit

The Early Termination visit corresponds to the last visit attended by subjects who discontinue from the study. Early Termination visits will be re-coded when possible. The related data will be summarized in the corresponding re-coded visit and in a visit named ‘*Early Termination*’. For example, if a subject discontinues with its last visit being the Day 28 visit, then the corresponding data will appear in the line ‘*Day 28, Post-Injection 1*’ and in the line ‘*Early Termination*’ of the summary tables.

Unscheduled Visit

Unscheduled visits will not appear in the summary tables, but in the listings.

Summary Statistics

Descriptive statistics for continuous variables and calculated change from baseline variables will include:

- number of subjects with available data
- mean and standard deviation
- median
- minimum and maximum

- 95% CI for mean, where indicated.

Categorical data and shift from baseline will be summarized by presenting:

- count
- percentage (where the denominator is based on the total number of subjects in the treatment group or overall, unless otherwise stated in the table footnotes)
- 95% CI for the proportion (Clopper-Pearson method), where indicated.

Protocol Deviations

Deviations from the protocol will be documented on an ongoing basis by the study monitors and project managers throughout the study. Protocol deviations are recorded outside the clinical database and will be reviewed by ThromboGenics during the course of the study, prior to database lock.

Missing Data

Missing data will not be replaced (unless otherwise specified), and data analysis will be performed based on the observed cases (OC) principle.

Subgroup Analysis

No subgroup analyses, nor analysis per center, will be performed.

Sensitivity Analysis

No sensitivity analyses will be performed.

Changes in Planned Analyses from the Protocol

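### The by-visit tables split post-injection 2 and 3 visits by injections received, with no whole-arm row in the written rule, and the two rows may overlap at Days 42 and 63

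*SAP*

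**What the plan says.** SAP section 3, By Visit Layout, states that "post-injection 2 and 3 visits will be presented on 2 rows". The first row "will present data of subjects with 2 or 3 injections, respectively". The second, labelled *Missing Repeat Injection(s)*, "will present data of subjects who did not receive the complete set of repeat injections". No third row for all subjects in the arm is named. The separate *Early Termination* line repeats the data of subjects who discontinue, so it is not a whole-arm row.

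Other parts of the plan bear on this:

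- **Analysis set (SAP 3).** There is one set: "The All Treated Subjects analysis set will include subjects who are randomized and receive the first injection of study treatment". The arm is fixed at the first injection.
- **Summary Statistics (SAP 3).** Means, SDs, medians, minimum and maximum are required. Percentages are given "where the denominator is based on the total number of subjects in the treatment group or overall", unless a table footnote says otherwise, with "95% CI for the proportion (Clopper-Pearson method), where indicated".
- **Protocol 3.1.1, 9.5.2 and 9.6.2.** BCVA change and total PVD are endpoints at each study visit. Exploratory proportions and mean letter changes are planned per treatment arm, and safety statistics by visit and arm.
- **Protocol 4.2.1.** No further injection is given after, among other events, a BCVA decrease of at least 15 "letters from baseline or BCVA worse than 20/400, in the study eye, at the time of repeat injection". Subjects withdrawn from repeat injection stay in follow-up.
- **SAP 1, Background.** "This document is an abbreviated version of the original SAP, which also contained mock-up tables and listings".

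**The concern.** A subject's row depends on what happened after randomisation. Some of the reasons for missing a repeat injection are tied to outcomes that the same tables report. A subject who loses 15 letters and is not re-injected leaves the first row of the BCVA table, and later BCVA values for that subject appear in the second row. Other reasons, such as pregnancy, emergency unmasking or the subject's own choice, need have no such link. The first row is therefore a selected part of the arm. Comparing first rows across arms is not a comparison of the randomised groups.

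The rows may also fail to partition the arm. The first row is tied to the visit by the word *respectively*. The second refers to a complete set of repeat injections without saying complete by when. If the two rows overlap, adding them counts some subjects twice.

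The final analysis has no tests and no sensitivity analyses, so the descriptive tables carry the exploratory efficacy and by-visit safety evidence.

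**Working it through.** The plan gives no figure to reproduce here. The check covers how many visits are affected, who falls in which row, and what can be rebuilt from two rows.

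**1. Visits affected** (Protocol 7.2.1, 7.2.2, 7.2.5 and Table 6). Injection 2 is at Day 35 and injection 3 at Day 70.

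| Measure | Post-baseline visits | Split for certain | Split if Months 9, 15, 24 count as post-injection 3 |
|---|---|---|---|
| BCVA | Days 7, 28, 42, 63, 77; Months 3, 9, 15, 24 (9) | Days 42, 63, 77; Month 3 (4) | 7 |
| Total PVD (B-scan and SD-OCT) | Days 28, 63, 77; Months 3, 9, 15, 24 (7) | Days 63, 77; Month 3 (3) | 6 |

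**2. Row membership.** Withdrawal from repeat injection is assessed at Day 28 and again at Day 63 (Protocol 4.2.1), so a subject can receive injection 2 and miss injection 3. Here the first row is read as requiring all injections due up to that visit.

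| Injections received | Days 42 and 63, complete set = those due so far | Days 42 and 63, complete set = both repeats | Day 77 onwards, either reading |
|---|---|---|---|
| 1, 2 and 3 | first row | first row | first row |
| 1 and 2 | first row | **both rows** | second row |
| 1 only | second row | second row | second row |

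From Day 77 the rows are disjoint and add to the arm. The overlap question concerns only two BCVA visits (Days 42 and 63) and one total PVD visit (Day 63).

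**3. What disjoint rows allow.** With row sizes n1, n2, means m1, m2 and SDs s1, s2:

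- whole-arm mean = (n1·m1 + n2·m2)/(n1 + n2)
- whole-arm sum of squares about the mean = (n1−1)s1² + (n2−1)s2² + [n1·n2/(n1+n2)]·(m1−m2)²

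Counts, minimum and maximum follow directly, and CIs can be recalculated. Under the default denominator, the two row percentages add to the arm percentage.

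**4. The median.** This example is constructed and deliberately extreme. Two possible first rows of 17 BCVA changes are:

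- A: −8, −8, −7, −7, −6, −6, −6, −6, 2, 3, 5, 8, 8, 10, 10, 12, 12
- B: −8, −8, −8, −8, −8, −7, −6, 2, 2, 2, 5, 7, 8, 9, 10, 12, 12

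Each sums to 16, so the mean is 16/17 = 0.94. Both have SD 7.94, median 2, minimum −8 and maximum 12, so the table row would be identical. Now add a second row of two subjects at −15:

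- mean: (16 − 30)/19 = −0.74 in both
- SD: 9.02 in both
- median (10th of 19 ordered values): −6 for A, +2 for B

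Identical table rows are therefore compatible with different whole-arm medians. The example shows that the median cannot be recovered; it does not show an expected size.

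**5. Size of double counting, if the rows overlap.** The protocol's clarification note gives 48 randomised. At 2:2:1 an ocriplasmin arm has 48 × 2/5 = 19.2, taken as n = 19. If k subjects sit in both rows and lie on average d letters from the arm mean, then

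rebuilt mean − true mean = k·d/(n + k).

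| k (assumed) | Sum of row n's | As % of arm | Shift for d = 5, 10, 15 letters (assumed) |
|---|---|---|---|
| 1 | 20 | 20/19 = 105.3% | 0.25, 0.50, 0.75 |
| 2 | 21 | 21/19 = 110.5% | 0.48, 0.95, 1.43 |

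The documents do not say how many subjects missed a repeat injection. If none did, the first row is the whole arm and the effect is nil.

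**The case against.** The strongest reply is that the public SAP leaves out the mock-up tables, which are where a total row or a footnote defining the second row would appear. That stands as a limit: the point concerns the written rule, and nothing here shows that the original SAP or the study report lacks a whole-arm result. But the rule specifies two rows, so confirmation is still needed.

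Secondly, the SAP also provides individual data listings, from which any median can be computed. That is true for someone who has the listings. The point about medians applies to a reader who has only the table rows.

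Thirdly, at Day 42 or 63 injection 3 is not yet due, so placing a subject in the missing-injection row would mean using a later event. The two rows were probably meant as complements. That is the more natural reading, but the text does not say so.

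Fourthly, two rows within an arm are still summaries by visit and arm, only finer. They are, but the planned arm-level figure is then not displayed. As for the link to outcome, BCVA loss maps directly onto a by-visit table. The link through another intraocular injection is looser, because anti-VEGF use is a cumulative endpoint to Month 15.

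Finally, only exploratory and descriptive tables are involved. That is accepted, and it limits the weight of the point.

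**Conclusion.** The concern holds for the rule as written, and it should be fixed. Post-injection 2 and 3 visits are shown on two rows defined by injections received, without a whole-arm row, and neither row alone estimates the arm. The scope is 4 to 7 of 9 post-baseline BCVA visits and 3 to 6 of 7 total PVD visits, depending on whether Months 9, 15 and 24 are split. Possible overlap is confined to Days 42 and 63.

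The size and direction of any difference between a row and its arm cannot be derived from the documents. The shifts of 0.25 to 1.43 letters rest on an assumed arm of 19, one or two subjects counted twice, and an assumed distance of 5 to 15 letters from the arm mean. Total PVD by Month 3 and the any-time safety proportions (Protocol 9.6.1) are not shown to be affected. Confidence is moderate because the mock-ups are not available.

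**What to change.** 1. In each by-visit table, show one all-treated row per arm and visit as the main display, or confirm that the mock-ups already have it. Keep the two existing rows as supplementary.
2. Define *Missing Repeat Injection(s)* by the injections due before the visit: injection 2 at Days 42 and 63, and injections 2 and 3 from Day 77. State that the first row is the complement, so that the rows are disjoint.
3. State whether Months 9, 15 and 24 are split.
4. Record in one sentence that the split departs from the protocol's by-arm summaries. It needs its own sentence because the SAP's list of changes covers only those caused by the early stop of enrolment.

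The cost is a few sentences of wording and one extra row per arm and visit, so the tables become slightly longer. No new data are needed, because subjects withdrawn from repeat injection remain in follow-up. As the SAP describes the final analysis as already done, the row can be added to the report tables.

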3. STUDY DESIGN AND METHODOLOGY

3.1. Study Endpoints

3.1.1. Efficacy Endpoints

Primary Efficacy Endpoint

- Total PVD by the Month 3 visit, confirmed on both B-scan ultrasound and SD-OCT (6mm), as assessed by the masked B-scan expert reader and the masked CRC, respectively

Exploratory Efficacy Endpoints

- A ≥ 2 -step progression on the International Clinical Diabetic Retinopathy Disease Severity Scale (ETDRS Severity Scale) from baseline, at Month 15 and at Month 24, based on 7-standard field stereo colour fundus photography, as assessed by the masked CRC
- Progression from NPDR at baseline to PDR (at least ETDRS level 61) at Month 15 and at Month 24, based on 7-standard field stereo colour fundus photography, as assessed by the masked CRC
- Improvement of ≥ 2 steps on the ETDRS Severity Scale from baseline, at Month 15 and at Month 24, based on 7-standard field stereo colour fundus photography, as assessed by the masked CRC
- Neovascularisation as compared to baseline, at Month 15 and at Month 24, based on 7-standard field stereo colour fundus photography, as assessed by the masked CRC
- Development or progression of macular oedema as compared to baseline, at each study visit, based on SD-OCT, as assessed by the masked CRC
- BCVA change from baseline at each study visit
- Total PVD at each study visit, confirmed on both B-scan ultrasound and SD-OCT (6mm), as assessed by the masked B-scan expert reader and the masked CRC, respectively
- Total PVD by the Month 3 visit, based on widefield SD-OCT, as assessed by the masked CRC, in a subset of sites where this is available
- Vitreous / pre-retinal haemorrhage by Month 24, based on 7-standard field stereo colour fundus photography, as assessed by the masked CRC
- Development of iris neovascularisation as compared to baseline, at each study visit, based on slit lamp examination
- PRP treatment by the Month 15 visit
- Anti-VEGF treatment by the Month 15 visit
- Vitrectomy by the Month 15 visit

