9. STATISTICS

9.1. Determination of Sample Size

One hundred and fifteen (115) subjects (46 subjects in each of the ocriplasmin arms and 23 subjects in the sham arm) will provide 80% power to detect a significant difference in total PVD rate by the Month 3 visit, for the comparison of sham to each of the ocriplasmin arms at a 2-sided alpha level of 0.05, assuming total PVD is achieved in 5% and 40% of the subjects in the sham and ocriplasmin arms, respectively. The sample size takes into account a drop-out rate of 10% by the Month 3 visit.

In order to protect the alpha level to 0.05, a hierarchical testing procedure will be used. Ocriplasmin 0.125mg will be first compared to sham. If the p-value of this first comparison is found < 0.05 , then ocriplasmin 0.0625mg will be compared to sham.

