9.3.2. Procedure for Accounting for Missing, Unused and Spurious Data

All reasonable efforts will be made to obtain complete data for all subjects. However, missing observations may occur due to subjects lost to follow-up or to noncompliance with required assessments. Management of dropouts and missing data will depend on their frequency and the nature of the outcome parameter.

The primary analysis of the efficacy parameters will be performed on the Full Analysis Set using the last-observation-carried-forward (LOCF), unless otherwise specified. Sensitivity analysis to evaluate the robustness of the data will be performed using alternative imputation method on the Full Analysis Set and the Per Protocol Set.

In the safety analysis, missing data will not be replaced and data analysis will be performed based on the Observed Case (OC) imputation method.

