9.5.2. Exploratory Efficacy Analyses

The analysis of exploratory dichotomous endpoints will be similar to the methodology used for the primary endpoint. For each exploratory endpoint, the proportion of subjects who achieve the endpoint at a certain study visit will be calculated in each treatment arm with corresponding 95% CI, stratified for NPDR severity at baseline. The adjusted differences in proportions between sham and each of the ocriplasmin arms will be calculated with their corresponding 95% CIs and tested using the Cochran-Mantel-Haenszel test. In addition, the effect of treatment on the proportion of subjects who achieve the endpoint will be computed using a logistic regression with effects for treatment and NPDR severity at baseline. Mean change from baseline in ETDRS

letters will be calculated by treatment arms at follow-up visits, stratified for NPDR severity at baseline. The adjusted differences in means between treatment arms will be summarised and analysed using a PROC GLM model including factors for treatment, BCVA at baseline and NPDR severity at baseline.

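### The PRP, anti-VEGF and vitrectomy endpoints by Month 15 are plain proportions that, under the published default denominator, count untreated early leavers as event-free and are biased low, modestly, when subjects withdraw

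*SAP*

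**What the plan says.** Protocol section 3.1.1 lists three cumulative endpoints among the exploratory ones: "PRP treatment by the Month 15 visit", "Anti-VEGF treatment by the Month 15 visit" and "Vitrectomy by the Month 15 visit". The SAP's list of changes to the planned analyses (end of section 3) drops five exploratory endpoints. These three are not among them, so they remain planned.

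On method, protocol section 9.5.2 states: "For each exploratory endpoint, the proportion of subjects who achieve the endpoint at a certain study visit will be calculated in each treatment arm". Section 9.3.2 had the efficacy analysis "using the last-observation-carried-forward (LOCF), unless otherwise specified". The SAP withdraws that imputation and all statistical testing, and plans no sensitivity analysis.

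What remains in SAP section 3 is a count, a percentage and, where indicated, a Clopper-Pearson interval. The rule for the percentage is "percentage (where the denominator is based on the total number of subjects in the treatment group or overall"; the sentence goes on to allow a different denominator where a table footnote says so. Under Missing Data the SAP says "Missing data will not be replaced (unless otherwise specified), and data analysis will be performed based on the observed cases (OC) principle". Neither document mentions censoring, a Kaplan-Meier estimate, person-time or a minimum follow-up for these endpoints.

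**The concern.** An endpoint of this kind accumulates over about 450 days, and an intervention given after a subject has left will usually not be recorded. If that subject stays in the denominator, the analysis in effect asserts that no intervention would have happened between leaving and Day 450. The resulting percentage underestimates the Month 15 risk, by more the more subjects leave and the earlier they do so.

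Withdrawal need not be equal between arms that receive real injections and an arm that receives a needle-free sham. If it is unequal, two arms with the same true risk will show different percentages, and the arm with more leavers will look as though it needed less treatment. With no testing and no sensitivity analysis, the descriptive percentages are what a reader of the report will compare.

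**Working it through.** **The plan's own figure.** The documents give no expected rate for these three endpoints. The only attrition figure is in protocol section 9.1: "The sample size takes into account a drop-out rate of 10% by the Month 3 visit". It fits the stated sample size. For 5% against 40%, 2:1 allocation, two-sided 0.05, 80% power and a continuity correction, the sham arm needs 20.67 evaluable subjects. Then 20.67/0.9 = 22.96, so 23; twice that is 45.93, so 46; and five times is 114.8, so 115. The figure covers Month 3 only and is a planning allowance, not an observed rate.

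**Assumptions.** R is the true risk by Month 15, the same in both arms. D is the probability of withdrawal by Month 15. Both hazards are constant and withdrawal is unrelated to outcome. I take R from 10% to 40%, and D = 10% in one arm against 20%, 30% or 40% in the other. None of these values comes from the documents.

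**Formula.** With T = 15 months, h = −ln(1−R)/T and m = −ln(1−D)/T, the expected percentage with all subjects in the denominator is

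F = h/(h+m) × [1 − exp(−(h+m)T)] = h/(h+m) × [1 − (1−R)(1−D)].

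Example, R = 30%:
- D = 10%: 0.3567/(0.3567+0.1054) × (1 − 0.63) = 0.772 × 0.37 = 28.6%.
- D = 30%: 0.5 × (1 − 0.49) = 25.5%.
- False difference: −3.1 points, although both arms truly have 30%.

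| True risk R | F at D=10% | F at D=20% | F at D=30% | F at D=40% | False difference against D=10% (D=20%, 30%, 40%) |
|---|---|---|---|---|---|
| 10% | 9.5% | 9.0% | 8.4% | 7.9% | −0.5, −1.1, −1.6 |
| 20% | 19.0% | 18.0% | 16.9% | 15.8% | −1.0, −2.1, −3.2 |
| 30% | 28.6% | 27.1% | 25.5% | 23.8% | −1.5, −3.1, −4.7 |
| 40% | 38.1% | 36.2% | 34.2% | 32.0% | −1.9, −4.0, −6.1 |

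**Check of the alternative.** A simulation of 400,000 subjects per scenario at R = 30% gave Kaplan-Meier estimates of 30.1% (D = 10%) and 30.0% (D = 30%). Under these assumptions the false difference disappears.

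**Scale.** The protocol's Clarification Note reports 48 subjects randomised. At 2:2:1 that is about 48 × 2/5 = 19.2 per ocriplasmin arm and 48/5 = 9.6 on sham. The Clopper-Pearson 95% interval for 3/10 is 6.7% to 65.2%, and for 6/19 it is 12.6% to 56.6%. A 6.1-point shift in an arm of 10 is about 0.6 of a subject.

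**The case against.** **The governing text may be unpublished.** The published SAP is abbreviated, and its denominator rule yields to table footnotes that cannot be seen. This stands as a limit: a footnote could change the denominator. But protocol section 9.5.2 is published and plans only proportions, and the SAP's list of changes adds no follow-up method.

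**A reader might infer that no simple proportion could be right.** That is too strong. If only subjects who attend Month 15 are analysed and withdrawal is unrelated to outcome, the proportion is unbiased; the same simulation gave 30.1% in both arms. This is an ordinary reading of observed cases, but the SAP does not state it for these endpoints.

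**A reader might also infer that observed cases means dropping event-free leavers while keeping leavers who had an event.** That would bias the percentage upwards: at R = 30%, to 32.6% with 20% withdrawal and 34.2% with 30%. The SAP states no such hybrid rule, so I do not rest the point on it.

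**A reader might infer that the arms will differ in withdrawal.** The documents do not show this. Protocol section 4.2.1 keeps subjects who stop repeat injections in full follow-up, and section 4.2.2 asks leavers to complete the exit procedures. The unequal rates above are a what-if.

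**The assumed risk may be too high for vitrectomy.** Protocol section 1.1.2 describes that operation as confined to advanced or macula-threatening disease. At R = 5%, 10% against 40% withdrawal gives 4.7% against 3.9%, a gap of 0.8 points. This is fair: the effect shrinks with the risk.

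**A raw count is a legitimate description, and a time-to-event estimate has its own assumption.** Both are true. Subjects may leave because they need treatment, which would bias a censored estimate as well. Hence the raw count should stay.

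**Conclusion.** The point holds in a limited form. Followed as published, with the default denominator, the three Month 15 intervention percentages are biased low whenever untreated subjects leave before Day 450, and unequal withdrawal carries that bias into the arm comparison. Under constant hazards, independent withdrawal, a true risk of 10% to 40%, and 10% against 20% to 40% withdrawal, the false difference is about 0.5 to 6 points. The documents supply neither rate at Month 15, so the size cannot be fixed more closely.

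It would be wrong to infer that a study conclusion or an error rate is at risk. The endpoints are exploratory, nothing is tested, and the bias is small against the sampling error with 48 subjects. The interval printed beside each percentage does not reflect the bias, though, and it is cheap to remove under the stated assumptions. This is an inexpensive improvement to descriptive reporting.

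**What to change.** In SAP section 3, add for each of the three endpoints:

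- Keep the raw count, and state its denominator and the number followed to Month 15 in each arm.
- Beside it, report the cumulative incidence at Day 450 per arm, measured from the first injection to the first recorded intervention of that type, censoring event-free subjects at last contact. Use Kaplan-Meier, or Aalen-Johansen with death as a competing event if there are deaths. Give the 95% CI and the number at risk.
- State how interventions with no start date are handled. The SAP's definition of concomitant interventions counts them, but Appendix 4.1 leaves a fully missing date unimputed, so they have no event time. Appendix 4.1 also moves a start date known only to the year of first injection to the injection date, which would put the event at Day 0; say whether that is intended here.
- Apply the Month 15 cut-off explicitly. The SAP's definition of concomitant interventions has none, and the final analysis runs to Month 24.

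The cost is a few lines of SAP text and one standard estimate per endpoint. The inputs are already collected: interventions at each visit (protocol section 6.4), start dates (used by the SAP to classify interventions) and withdrawal dates (protocol section 4.2.2). The downside is that the estimate assumes withdrawal is unrelated to the need for treatment, and late estimates will be imprecise in a sham arm of about 10.
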